3.9.2	National Eye Institute Visual Functioning Questionnaire	31
3.10	Interim Analysis	33
3.11	Sample Size Justification.....	33

4	REFERENCES	35
5	APPENDIX.....	36
5.1	Sample SAS Code for Primay endpoint analysis.....	36

DOCUMENT HISTORY

Version	Author	Description
1.0	[REDACTED]	New Document
2.0	[REDACTED]	Additional clarification added [REDACTED] [REDACTED] Additional minor updates. [REDACTED] [REDACTED]

LIST OF ABBREVIATIONS

AE	Adverse Event
ANCOVA	Analysis of Covariance
BSCVA	Best Spectacle Corrected Visual Acuity
CRF	Case Report/Record Form
CSR	Clinical Study Report
CXL	Corneal Collagen Cross-Linking
D	Diopter
ECC	Endothelial Cell Count
ETDRS	Early Treatment of Diabetic Retinopathy Study
ICH	International Conference on Harmonization
IOP	Intraocular Pressure
ITT	Intent to Treat
K _{max}	Maximum Keratometry
LOCF	Last Observation Carried Forward
MAR	Missing at Random
██████	████████████████████
MedDRA	Medical Dictionary for Regulatory Activities
MRSE	Manifest Refraction Spherical Equivalent
NEI-VFQ 25	National Eye Institute Visual Functioning Questionnaire
OCT	Optical Coherence Tomography
██████	████████████████████
PP	Per Protocol

PT

Preferred Term

██████

████████████████████

SAE

Serious Adverse Event

SAP

Statistical Analysis Plan

SOC

System Organ Class

TEAE

Treatment-Emergent Adverse Event

UCVA

Uncorrected Visual Acuity

1 INTRODUCTION

This study is a multicenter, randomized, sham-controlled evaluation of the safety and efficacy of epithelium-on corneal collagen cross-linking (CXL) for the treatment of progressive keratoconus. The objectives of this study are to evaluate the safety and efficacy of epithelial-on corneal collagen cross-linking in impeding the progression of, and/or reducing maximum corneal curvature (K_{\max}) in eyes with progressive keratoconus.

This Statistical Analysis Plan (SAP) describes data-handling and statistical procedures to be used for the analysis and reporting of efficacy and safety data collected under Avedro Protocol ACP-KXL-308 (version 11 Oct 2018) and presented in the clinical study report (CSR). They are based on those presented in Section 10, Statistical Hypotheses and Methods of Analyses, of the study protocol. Any post-hoc or exploratory analyses not specified in this SAP will be identified as such when they are presented in the CSR. This SAP will have been developed and finalized prior to locking the clinical database.

The SAP was written in accordance with the recommendations outlined in the International Conference on Harmonisation (ICH) E9 Guideline entitled “Guidance for Industry: Statistical Principles for Clinical Trials” and the ICH-E3 Guideline, entitled “Guidance for Industry: Structure and Content of Clinical Study Reports.”

2 STUDY SUMMARY

2.1 STUDY OBJECTIVES

The objectives of this study are to evaluate the safety and efficacy of epithelial-on corneal collagen cross-linking in impeding the progression of, and/or reducing maximum corneal curvature (K_{\max}) in eyes with progressive keratoconus.

2.2 STUDY DESIGN

This study is a multicenter, randomized, sham-controlled evaluation of the safety and efficacy of epithelium-on corneal collagen cross-linking (CXL) for the treatment of progressive keratoconus. Each subject will have at least one eye randomized to either the CXL Treatment group or the Sham Treatment/Control group. If both eyes meet the eligibility criteria, both eyes may be enrolled in the study, however one eye will be treated first and the second eye treated [REDACTED] after the first eye.

Two treatment regimens will be tested using the following combinations of riboflavin ophthalmic solution(s) and UVA:

Treatment 1 (CXL Treatment)

- [REDACTED] riboflavin ophthalmic solution [REDACTED] + [REDACTED] riboflavin ophthalmic solution [REDACTED]
- UVA irradiation [REDACTED] [REDACTED]
- Supplemental oxygen

Treatment 2 (Sham Treatment)

- 0.0% riboflavin ophthalmic solution ([REDACTED] Placebo)
- UVA [REDACTED] [REDACTED]

2.2.1 Number of Study Eyes

Up to 275 study eyes with progressive keratoconus (183 in CXL Treatment group and 92 in the Sham Treatment group) will be randomized to provide at least 160 and 80 evaluable eyes in the CXL Treatment group and Sham Treatment group, respectively, at the 6 and 12 month follow-up examinations.

2.2.2 Randomization and Masking Procedures

[REDACTED]
[REDACTED] Randomization between the CXL Treatment group and Sham Treatment/Control group will be in a 2:1 ratio within each stratum.

[REDACTED]
[REDACTED]
[REDACTED]

The following assessments will be conducted by a masked examiner who will not be aware of which treatment has been performed:

- Best Spectacle Corrected Visual Acuity (BSCVA) at Months 1, 3, 6, and 12
- Uncorrected Visual Acuity (UCVA) at Months 1, 3, 6, and 12
- Manifest Refraction at Months 1, 3, 6, and 12.

The masked examiner will not have access to the subject’s medical and/or study records which would unmask him/her to the study treatment. The masked examiner will not conduct any study examinations on that subject beyond the visual measurements indicated with the endpoint assessment.

[REDACTED] [REDACTED]
[REDACTED]

[REDACTED]
[REDACTED]
[REDACTED]

[REDACTED]

2.2.4 Efficacy Assessments

2.2.4.1 Maximal corneal curvature

The maximum corneal curvature (K_{max}) is the maximum keratometry at the apex of the cone, measured on the Pentacam corneal topography image. It is assessed at the following visits:

- Visits 1 (Day -45 to -1)
- Visit 6 (1 month)
- Visit 7 (3 months)
- Visit 8 (6 months)
- Visit 9 (12 months).

2.2.4.2 Manifest Refraction Spherical Equivalent

The Manifest Refraction Spherical Equivalent (MRSE) will be evaluated at baseline and each follow-up exam beginning at 1 month. MRSE is calculated as: $MRSE = \text{sphere} + 1/2 \text{ cylinder}$.

2.2.4.3 Visual Acuity (BSCVA and UCVA)

The number of letters read from the Early Treatment of Diabetic Retinopathy Study (ETDRS) chart from the BSCVA and UCVA will be evaluated at screening, baseline, and each follow-up exam beginning at 1 month.

2.2.5 Safety Assessments

A primary safety assessment is the BSCVA assessed at the following visits:

- Visits 1 (Day -45 to -1)
- Visit 6 (1 month)
- Visit 7 (3 months)
- Visit 8 (6 months)
- Visit 9 (12 months).

The incidence of serious ophthalmic adverse events (AEs) is also a primary safety assessment.

The following are additional safety assessments:

- Adverse events
- Slit lamp biomicroscopy
- Pentacam Pachymetry
- Intraocular pressure using Goldmann applanation tonometry
- Manifest refraction
- Dilated fundus exam
- Endothelial cell counts
- Macular optical coherence tomography.

2.2.6 Other Assessment(s)

2.2.6.1 Anterior Segment OCT

Anterior segment optical coherence tomography will be performed at Screening, 1, 3, 6, and 12 month examinations.

2.2.7 Questionnaires

2.2.7.1 National Eye Institute Visual Functioning Questionnaire

The self-administered version of the National Eye Institute Visual Functioning Questionnaire (NEI-VFQ 25) will be administered at screening to establish the subject's baseline and at the 1, 3, 6 and 12 month examinations.

2.2.8 Schedule of Events

The Schedule of Events is presented in [Table 1](#).

Table 1. Schedule of Events

Procedure	Screen	Treatment	POST-TREATMENT VISITS ¹³						
			1 DAY	3 Day	1 WK	1 MO	3 MO	6 MO	12 MO
	Visit 1	Visit 2	Visit 3	Visit 4	Visit 5	Visit 6	Visit 7	Visit 8	Visit 9
	Day -45 to -1	Day 0	Day 1 to 2	Day 3 to 4	Day 5 to 14	Day 21 to 42	Day 84 to 98	Day 180 to 210	Day 360 to 390
Informed Consent/Assent	X								
Medical & Medication History ¹	X	X	X	X	X	X	X	X	X
Demographics	X								
BSCVA ²	X					M ¹¹	M ¹¹	M ¹¹	M ¹¹
UCVA ²	X		X	X	X	M ¹¹	M ¹¹	M ¹¹	M ¹¹
Manifest Refraction	X					M ¹¹	M ¹¹	M ¹¹	M ¹¹
Intraocular Pressure Measurement ³	X					X	X	X	X
Slit Lamp Exam	X	X ⁹	X	X	X	X	X	X	X
Dilated Fundus Examination ⁴	X						X	X	X
Pentacam Tomography and Pachymetry ⁵	X					X	X	X	X
Ultrasound Pachymetry		X ¹⁰							
Endothelial Cell Count ⁶	X						X	X	X
Macular and anterior segment OCT ⁷	X					X ¹²	X	X	X
NEI-VFQ 25	X					X	X	X	X
Adverse Event Query		X	X	X	X	X	X	X	X
Study Treatment		X							
Pregnancy Test ⁸		X							

- ¹ Ocular status and/or history including history of contact lens wear. Non-specific questioning should be used at each visit to determine other vision-related complaints, complications, or adverse events.
- ² Distance BSCVA and UCVA will be performed using a calibrated ETDRS eye chart and recording the total number of letters that are read correctly.
- ³ Intraocular pressure measurement by Goldmann applanation tonometry at the slit lamp. A Tonopen or Pneumotonometer may be used only if applanation tonometry is medically contraindicated or deemed to be unreliable. Contraindication must be documented in the subject's chart.
- ⁴ The status of the lens, optic disc (including cup/disc ratio), macula, retinal vessels and peripheral retina should be examined.
- ⁵ Pentacam measurements are performed using the Pentacam HR [REDACTED]
[REDACTED]
[REDACTED]
[REDACTED]
- ⁶ Endothelial cell counts will be obtained via specular microscopy. [REDACTED]
[REDACTED]
- ⁷ Anterior segment and macular optical coherence tomographies (OCTs) will be performed [REDACTED]
[REDACTED]
[REDACTED]
- ⁸ Females capable of becoming pregnant must have urine pregnancy testing performed prior to randomization of the study eye [REDACTED]; must not be lactating, and must agree to use a medically acceptable form of birth control for at least one week prior to the randomization visit, [REDACTED] and continue to use the method for one month following [REDACTED] treatment.
- ⁹ Slit lamp exam on treatment day should be performed prior to randomization and immediately following treatment.
- ¹⁰ Ultrasound pachymetry should be performed on Treatment day after completion of the riboflavin ophthalmic solutions, prior to initiating UV treatment.
- ¹¹ Measurements indicated by an "M" will be conducted by a masked examiner who will not be aware of which treatment has been performed. The masked examiner should not conduct any study examinations on that subject beyond the assessments indicated with the "M".
- ¹² Only anterior segment OCT is required at Visit 6 (Month 1).
- ¹³ Subject needs to complete all follow-up visits with the investigator and/or study team on site.

3 STATISTICAL METHODS

3.1 GENERAL METHODS

3.1.1 Computing Environment

All statistical analyses will be performed using SAS® Version 9.4 or higher for Windows.

3.1.2 Reporting of Numerical Values

All clinical study data will be presented in patient data listings. Descriptive statistics (n, mean, standard deviation, median, minimum, and maximum) will be calculated by treatment group for continuous variables. Descriptive statistics for categorical variables will include number and percentage of subjects or eyes, as appropriate. Confidence intervals will be provided where appropriate.

Means, medians, and confidence intervals will be reported to one decimal place. Standard deviations will be reported to two decimal places. Minimum and maximum will be reported to the same number of decimal places displayed on the Case Report/Record Form (CRF) or by the laboratory/vendor. P-values will be reported to 4 decimal places.

All testing and confidence intervals will use a two-sided significance level of 5% unless otherwise specified.

3.1.3 Baseline Value and Change from Baseline

Baseline value is defined as the most recent non-missing value obtained immediately prior to administration of the test article [REDACTED]. Change from baseline will be calculated by subtracting the baseline value from the post-dose assessment for each study eye (i.e., post-dose – baseline).

[REDACTED]
[REDACTED]
[REDACTED]

[REDACTED] [REDACTED]
[REDACTED]

[REDACTED]
[REDACTED]
[REDACTED]
[REDACTED]
[REDACTED]
[REDACTED]

[REDACTED]

3.2 HANDLING OF MISSING/INCOMPLETE VALUES

Missing data can reduce the statistical power of a study and produce biased estimates leading to invalid conclusions. Therefore, every effort will be made to ensure complete, accurate, and timely data collection, to avoid missing data. Missing clinical outcome data can occur for multiple reasons, including missed subject visits and scales or measures with missing item scores. Missing and incomplete data will be identified for investigation and possible resolution by Data Management prior to the study database lock.

[REDACTED]

Based on a similar study conducted by Avedro, study UVX-002 (*NDA 203-324, UVX-002 Table 14.2.1.1.1*), the percentage of missing data for the Month 6 K_{max} change from baseline endpoint in the CXL group was 8%. It is anticipated the rate of missing data for this study will be similar to the 8% rate for both the CXL and sham treatment groups.

To assess the pattern of missing data, any missing observations for the primary efficacy endpoint will be described in detail and evaluated for assessment of possible bias. For each of the two treatment groups, 95% confidence intervals for the difference in means or proportions stratifying on missing/not-missing the primary endpoint will be performed for the following baseline demographics and characteristics:

- Age
- Sex (female / male)
- Race (white / non-white)
- Ethnicity (Hispanic / non-Hispanic)
- Baseline keratoconus disease severity [REDACTED]

3.2.1 Multiple Imputation

Multiple imputation will be the method for handling missing data in the primary efficacy endpoint analysis (i.e., the primary endpoint is the Month 6 change from baseline in K_{max}). [REDACTED]

[REDACTED]

The MAR assumption implies that the covariates in the model can account for differences in the distribution of missing variables for observed and missing cases.

[REDACTED]

[REDACTED] However, to assess the robustness of this MAR assumption, multiple sensitivity analyses will be performed, including an analysis which assumes the primary endpoint missing data pattern is Missing Not at Random (MNAR).

[REDACTED]

[REDACTED] The initial imputation to produce a monotonic missing data pattern for the MNAR

imputation will be performed by using the same method as described for the MAR imputation.

3.2.2 Observed Case

Observed Case will be used for supplemental analysis of the primary efficacy endpoint analysis. Observed Case analyses will be based on the study eyes with non-missing values.

3.2.3 Last Observation Carried Forward

Last Observation Carried Forward (LOCF) will be used for supplemental analysis of the primary efficacy endpoint analysis. For the LOCF analyses, if a study eye is missing the analysis value, the post-baseline value most recent to the missing observation will be imputed for the analysis.

[Redacted text block containing multiple paragraphs of blacked-out content]

3.3 ANALYSIS POPULATIONS

3.3.1 Intent-to-Treat Population

The intent-to-treat (ITT) population includes all randomized study eyes that had at least one post-treatment follow-up efficacy assessment. The ITT population is designated as the primary population for all efficacy analyses.

3.3.2 Safety Population

The safety population is comprised of all study eyes that received the study treatments [REDACTED]. [REDACTED]

The safety population will be used for the analysis of the safety endpoints.

For the safety analyses where patient is the unit of analysis, a patient will be in the CXL treatment group if either study eye is in the CXL treatment group. If a patient has both eyes in the control group, or only one eye in the study and that eye is in the control group then that patient will be in the Control group.

The following additional Safety Populations will also be used.

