7.1.2 Allocation of Study Treatment

Subjects will be considered enrolled in the study once they have signed the informed consent form and been randomized. Study eyes of subjects that meet all the inclusion criteria and none of the exclusion criteria will be randomized to either the CXL Treatment group or the Sham Treatment/Control Group in a 2:1 allocation ratio. [REDACTED]

[REDACTED]

Randomization will occur immediately prior to cross-linking or sham treatment per Section 8.2.2.

Subjects with bilateral keratoconus in which both eyes qualify for the study may have both eyes designated as study eyes by the Investigator; each eligible eye will be randomized independently. One eye will undergo the study procedure first. The second eye can be randomized to undergo the study procedure between the Week 1 and Month 3 visits for the first eye.

Subjects may be re-screened if they are not randomized within 45 days of screening examinations, or if they have a history of progressive keratoconus but do not meet the progression criteria (as outlined in inclusion criterion # 7) at the time of initial screening. Subjects who fail to meet any of the other eligibility criteria (do not meet any other inclusion criteria or meet any exclusion criteria) cannot be re-screened and will be documented as screen failures. Subjects who are re-screened will retain their assigned subject number.

A [redacted] randomization scheme [redacted] [redacted] [redacted] will not be revealed to the participating Investigators or study site personnel.

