8.6 Subject Study Duration

The expected study duration for each subject following treatment is approximately 12 months when only one eye receives the study treatment. For subjects that receive study treatment in both eyes, the study duration may be approximately 15 months.

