3.3.2.2 Safety Population – All CXL Treated Patients

This population consists of patients who received the CXL procedure (in either or both eyes). In the safety analyses which use this population a patient’s “baseline” will be the last observation prior to when the patient first receives the CXL procedure in either eye.

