3.8.2 Adverse Events

Treatment Emergent adverse events (TEAEs) will be summarized by treatment group and categorized by system organ class (SOC) and preferred term (PT) using the Medical Dictionary for Drug Regulatory Affairs (MedDRA 15.1 or higher). TEAEs are adverse events (AEs) which occurred after study treatment administration or pre-existing AEs that worsened after study treatment administration.

The number and percentage of subjects reporting non-ocular AEs will be tabulated by body system and preferred term within each treatment and overall. The number and percentage of study eyes reporting ocular AEs will be tabulated by preferred term

within each treatment group and overall. The number of subjects/study eyes reporting AEs will also be summarized by relationship to the test article as well as severity of AEs. Serious adverse event (SAEs) will also be summarized by group and categorized by SOC and PT. An AE with a relationship to the test article of Possible, Probable, or Definite will be considered “Related”.

AEs will be summarized over the following time periods based on the onset date of the TEAE:

- Baseline to Month 3: TEAEs with an onset date up to and including the Month 3 visit
- Baseline to Month 6: TEAEs with an onset date up to and including the Month 6 visit
- Study Period: All TEAEs.

For the presentation of AE incidences, the SOCs will be sorted alphabetically, and within SOC, the preferred term (PT) will be used and presented by decreasing total frequency.

The incidence of serious ophthalmic adverse events will be summarized by treatment group and presented in a listing.

Ocular and non-ocular AEs will be summarized separately. Each of these adverse event summaries will be provided for:

- Non-ocular AEs (Subject Level):
 - [Redacted]
 - [Redacted]
- Ocular adverse events (Study Eye Level):
 - [Redacted]

- [REDACTED]
- [REDACTED]

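### Patient-level safety tables count any patient with one CXL eye as CXL, so the CXL column is enriched for two-eye patients and takes in some pre-CXL sham time

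*SAP*

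**What the plan says.** SAP 3.3.2 sets the group for safety analyses in which the patient is the unit: "a patient will be in the CXL treatment group if either study eye is in the CXL treatment group". The Control group is the remainder: "If a patient has both eyes in the control group, or only one eye in the study and that eye is in the control group". No mixed category is visible.

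Protocol 7.1.2 allocates eyes "in a 2:1 allocation ratio" and, for bilateral patients, states that "each eligible eye will be randomized independently". The procedures are staggered: "The second eye can be randomized to undergo the study procedure between the Week 1 and Month 3 visits for the first eye". Protocol 8.6 puts one-eye participation at about 12 months and adds: "For subjects that receive study treatment in both eyes, the study duration may be approximately 15 months".

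SAP 3.8.2 counts treatment-emergent AEs from administration of study treatment, which includes sham. It tabulates ocular AEs by study eye and non-ocular AEs by subject, the latter under a label beginning "Non-ocular AEs (Subject Level". Its summary periods end at the Month 3 visit, at the Month 6 visit, or cover the whole study.

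SAP 3.3.2.2 adds an All CXL Treated Patients population, whose baseline is "the last observation prior to when the patient first receives the CXL procedure in either eye".

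**The concern.** Eyes are randomised, but these tables count patients. Under an either-eye rule the patient's column depends on how many eyes were enrolled as well as on the treatment drawn. Two-eye patients have two procedures and up to about three months' more participation, so they have more opportunity to report an event whatever the treatment does.

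Separately, a patient whose first eye is sham and whose second eye is CXL sits in the CXL column from the first procedure. Non-ocular events in the interval before any CXL are reported as CXL events.

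At stake is how the non-ocular AE table is read. Part of any difference between columns could come from the grouping rule. The direction is not fixed: extra exposure tends to raise CXL incidence, while sham-only time in mixed patients can dilute a real CXL effect.

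**Working it through.** **Inputs.** Allocation of 2/3 to CXL per eye, independent between eyes (Protocol 7.1.2). Grouping rule (SAP 3.3.2). 275 eyes (SAP 2.2.1). The share of patients enrolling both eyes, *b*, is not given in the visible text, so 10%, 30% and 50% are assumed.

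**Plan's own figure.** 275 × 2/3 = 183.3 and 275 × 1/3 = 91.7, which reproduces the SAP's 183 and 92 eyes. The documents give no patient-level split.

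**Probability of each column.**
- One eye: CXL 2/3, Control 1/3.
- Two eyes: both CXL 4/9, one of each 4/9, both sham 1/9. So CXL group = 1 − (1/3)² = 8/9 and Control = 1/9.

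**Composition of the columns.** Patients = 275/(1+*b*).
- CXL fraction C = (2/3)(1−*b*) + (8/9)*b*; Control fraction S = (1/3)(1−*b*) + (1/9)*b*.
- Bilateral share: (8/9)*b*/C in CXL, (1/9)*b*/S in Control.
- Mixed share of CXL: (4/9)*b*/C. Half of these are sham-first: (2/9)*b*/C.

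| *b* | Patients | CXL : Control | Bilateral in CXL | Bilateral in Control | Mixed, of CXL | Sham-first, of CXL |
|---|---|---|---|---|---|---|
| 10% | 250.0 | 172.2 : 77.8 = 2.21 | 12.9% | 3.6% | 6.5% | 3.2% |
| 30% | 211.5 | 155.1 : 56.4 = 2.75 | 36.4% | 12.5% | 18.2% | 9.1% |
| 50% | 183.3 | 142.6 : 40.7 = 3.50 | 57.1% | 25.0% | 28.6% | 14.3% |

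A simulation at *b* = 30% agreed (36.4% and 12.5% bilateral).

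**Effect on AE rates with no true treatment effect.** Assume *b* = 30% and a constant hazard giving 10% non-ocular AE risk in 6 months. If the Month 6 window runs to the later eye's Month 6 visit and the gap between procedures is *g* months, a bilateral patient's risk is 1 − 0.9^((6+*g*)/6).
- *g* = 1: bilateral risk 11.57%. CXL = 0.636 × 10% + 0.364 × 11.57% = 10.57%; Control = 0.875 × 10% + 0.125 × 11.57% = 10.20%. Ratio 1.04.
- *g* = 3: bilateral risk 14.62%. CXL 11.68%, Control 10.58%. Ratio 1.10.
- Gap of one week: ratio about 1.01.
- Window closing at the first eye's Month 6 visit: all patients have the same window, ratio 1.00.

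The visible SAP does not say which eye's visit closes the window. A different assumption, 10% risk attached to each procedure rather than to time, gives 13.27% against 11.13%, ratio 1.19. The documents do not establish which model is right.

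**Would a mixed column alone suffice?** Bilateral share among CXL-only patients is (4/9)*b* / [(2/3)(1−*b*) + (4/9)*b*]. At *b* = 30% this is 0.1333/0.6000 = 22.2%, against 12.5% in the sham-only column. The gap narrows but stays.

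**Grouping by the first-treated eye's arm.** At *b* = 30%: 211.5 × 2/3 = 141.0 against 70.5 patients, with an expected 30% bilateral in each, provided second-eye enrolment does not depend on first-eye treatment.

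**The case against.** The strongest reply is that the reach is narrow. The rule applies only where the patient is the unit. Under the SAP, ocular AEs are counted by study eye and BSCVA loss is an eye-level measure, so the two primary safety endpoints (SAP 3.4.4) do not pass through it. AE incidence is descriptive and no test of non-ocular rates is visible. All of this stands.

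A reader might infer that every SAE comparison is compromised. The documents do not support that: SAP 3.8.2 states no unit for the SAE summary, so it is affected only if SAEs are counted by subject. A reader might also infer that a planned randomised inference fails. None is planned on these tables.

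Next, the All CXL Treated Patients population resets baseline at the first CXL, so pre-CXL sham time can be separated there. This reduces the misattribution but does not repair the SAP 3.3.2 tables, because that population has no sham comparator.

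Counting any exposed patient as exposed is also a recognisable pre-specified safety choice, and the distortion is small beside sampling error. With about 155 and 56 patients and 10% incidence, the standard error of the log risk ratio is √[9 × (1/155 + 1/56)] = 0.47, a 95% interval of roughly a factor of 2.5 either way. That limits the practical weight of the point. It does not justify an avoidable imbalance.

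Finally, parts of SAP 3.3.2 and both items under the non-ocular label in SAP 3.8.2 are blacked out and may add handling. The visible two-group rule nevertheless assigns every patient and leaves no mixed category.

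**Conclusion.** The point holds for patient-level safety summaries: visibly the non-ocular AEs, and SAEs if counted by subject. The dependence of column on number of eyes follows from the stated rule and the independent 2:1 randomisation, for any bilateral share between 0 and 1. Its size depends on that unstated share, hence the 10% to 50% range.

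The consequence for AE rates is modest and rests on assumptions: a ratio of about 1.00 to 1.10 at 30% bilateral under the constant-hazard model, depending on the gap and on which eye's Month 6 visit closes the window. The per-procedure figure needs a further assumption and is not relied on.

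It would be tempting to conclude that the safety comparison as a whole is invalid, or biased in a known direction. Neither follows. The eye-level safety analyses in the SAP are not affected, and the two mechanisms can pull in opposite directions. Protocol 10.8.1 does tabulate ocular AEs by subject, where the SAP uses study eyes; if the protocol's unit were used, the reach would be wider, so the two passages should be reconciled. If blacked-out text already separates mixed patients, the sponsor need only confirm it.

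**What to change.** In SAP 3.3.2, present subject-level AE tables in three exclusive columns: CXL eye(s) only, sham eye(s) only, and one of each. Give person-time at risk in every column, and in the mixed column split events into before and after the first CXL procedure. State in SAP 3.8.2 which eye's visit closes the Month 3 and Month 6 windows for a bilateral patient, and the unit for the SAE summary.

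Because the single-treatment columns remain unbalanced for bilateral enrolment, add a supportive tabulation by the randomised arm of the first-treated eye, from that eye's Day 0 to the earlier of second-eye treatment or Month 6. This should not be the main table: it drops bilateral exposure and later CXL exposure in sham-first patients, and the censoring may be informative if second-eye enrolment depends on experience with the first eye. Keep the existing any-CXL grouping and the All CXL Treated Patients table.

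The cost is SAP wording, an extra column and one extra table, with no change to conduct or data collection. The drawback is that the supportive table excludes events after second-eye treatment, which remain visible in the three-column table.
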